8.4.2 Method of Detecting AEs, SAEs, and Other Reportable Safety Events

Care will be taken not to introduce bias when detecting AEs and/or SAEs and other reportable safety events. Open-ended and nonleading verbal questioning of the participant is the preferred method to inquire about AE occurrence.

8.4.3 Follow-up of AE, SAE, and Other Reportable Safety Event Information

After the initial AE/SAE report, the investigator is required to proactively follow each participant at subsequent visits/contacts. All AEs, SAEs, and other reportable safety events, including pregnancy and exposure during breastfeeding, ECIs, cancer, and overdose will be followed until resolution, stabilization, until the event is otherwise explained, or the participant is lost to follow-up (as defined in Section 7.3). In addition, the investigator will make every attempt to follow all nonserious AEs that occur in randomized participants for outcome. Further information on follow-up procedures is given in Appendix 3.

8.4.4 Regulatory Reporting Requirements for SAE

Prompt notification (within 24 hours) by the investigator to the Sponsor of SAE is essential so that legal obligations and ethical responsibilities towards the safety of participants and the safety of a study intervention under clinical investigation are met.

The Sponsor has a legal responsibility to notify both the local regulatory authority and other regulatory agencies about the safety of a study intervention under clinical investigation. The Sponsor will comply with country-specific regulatory requirements and global laws and regulations relating to safety reporting to regulatory authorities, IRB/IECs, and investigators.

Investigator safety reports must be prepared for SUSARs according to local regulatory requirements and Sponsor policy and forwarded to investigators as necessary.

An investigator who receives an investigator safety report describing an SAE or other specific safety information (eg, summary or listing of SAE) from the Sponsor will file it along with the IB and will notify the IRB/IEC, if appropriate according to local requirements.

8.4.5 Pregnancy and Exposure During Breastfeeding

Although pregnancy and infant exposure during breastfeeding are not considered AEs, any pregnancy or infant exposure during breastfeeding in a participant (spontaneously reported to the investigator or their designee) that occurs during the study are reportable to the Sponsor.

All reported pregnancies must be followed to the completion/termination of the pregnancy. Pregnancy outcomes of spontaneous abortion, missed abortion, benign hydatidiform mole, blighted ovum, fetal death, intrauterine death, miscarriage, and stillbirth must be reported as serious events (Important Medical Events). If the pregnancy continues to term, the outcome (health of infant) must also be reported.

8.4.6 Disease-related Events and/or Disease-related Outcomes Not Qualifying as AEs or SAEs

Efficacy endpoints, as outlined in this section, will not be reported to the Sponsor, as described in Section 8.4.1.

Specifically, the suspected/actual events covered in this exception include any event that is disease progression of the cancer under study.

The Sponsor will monitor unblinded aggregated efficacy endpoint events and safety data to ensure the safety of the participants in the study. Any suspected endpoint that upon review is not progression of the cancer under study will be forwarded to Global Pharmacovigilance as an SAE within 24 hours of determination that the event is not progression of the cancer under study.

8.4.7 Events of Clinical Interest

Selected nonserious and SAEs are also known as ECIs and must be reported to the Sponsor.

[figure not shown]
Events of clinical interest for this study include:

1. An overdose of Sponsor's product, as defined in Section 8.5.
2. An elevated AST or ALT lab value that is greater than or equal to $3 \times$ ULN and an elevated total bilirubin lab value that is greater than or equal to $2 \times$ ULN and, at the same time, an alkaline phosphatase lab value that is less than $2 \times$ ULN, as determined by way of protocol-specified laboratory testing or unscheduled laboratory testing.*

[figure not shown]
*Note: These criteria are based upon available regulatory guidance documents. The purpose of the criteria is to specify a threshold of abnormal hepatic tests that may require an additional evaluation for an underlying etiology. The study site guidance for

assessment and follow-up of these criteria can be found in the Investigator Study File Binder (or equivalent).

CCI

CCI

CCI

8.10 Visit Requirements

Visit requirements are outlined in Section 1.3. Specific procedure-related details are provided in Section 8.

8.10.1 Screening

Approximately 28 days prior to treatment randomization, potential participants will be evaluated to determine that they fulfill the entry requirements as set forth in Section 5.

Subjects may be rescreened after initially failing to meet the inclusion/exclusion criteria. Results from assessments performed during the initial screening period are acceptable in lieu of a repeat screening test if performed within the specified time frame and the inclusion/exclusion criteria are met.

Documented informed consent must be obtained prior to performing any protocol-specific procedure. Results of a test performed prior to the participant providing documented informed consent as part of routine management are acceptable in lieu of a screening test if performed within the specified time frame. Screening procedures are to be completed within 28 days prior to the first dose of study intervention except for the following:

- Laboratory tests are to be performed within 7 days prior to the first dose of study intervention. An exception is hepatitis and thyroid function testing, which may be done up to 28 days prior to the first dose of study intervention.
- Evaluation of ECOG is to be performed within 7 days prior to the first dose of study intervention.
- For women of reproductive potential, a urine or serum pregnancy test will be performed within 24 hours prior to the first dose of study intervention. If urine pregnancy results cannot be confirmed as negative, a serum pregnancy test will be required (performed by the local study site laboratory). Refer to Appendix 7 for country-specific requirements.
- Tumor tissue testing for PD-L1 status (all participants) and HPV status (oropharyngeal cancer participants) are required for stratification prior to randomization. The sample should be sent to the central laboratory at least 14 days prior to randomization, unless testing locally (see Procedures Manual for details regarding tumor tissue collection). If testing locally, or reporting HPV status by history, tumor p16 expression must be evaluated by assessment of IHC analysis with CINtec® p16 Histology assay (Ventana Medical Systems Inc., Tucson AZ) using the “Benchmark Ultra” autostainer (Ventana, Tucson, AZ) and standard protocol.

8.10.2 Treatment Period Visit

Visit requirements are outlined in the SoA (Section 1.3). Specific procedure-related details are provided in Section 8.1.

8.10.3 Discontinued Participants Continuing to be Monitored in the Study

The Discontinuation Visit should occur at the time study intervention is discontinued for any reason. If the Discontinuation Visit occurs 30 days from the last dose of study intervention, at the time of the mandatory Safety Follow-up Visit, the Discontinuation Visit procedures and any additional Safety Follow-up procedures should be performed. Visit requirements are outlined in Section 1.3. Additional details regarding participant withdrawal and discontinuation are presented in Section 7.

8.10.3.1 Safety Follow-up Visit

The mandatory Safety Follow-up Visit should be conducted approximately 30 days after the last dose of study intervention or before the initiation of a new anticancer treatment, whichever comes first.

All AEs that occur prior to the Safety Follow-up Visit should be recorded up to 30 days following EOT.

8.10.3.2 Imaging Follow-up Visits

Participants who discontinue study intervention for reasons other than documented PD should continue with imaging assessments per the protocol-defined schedule until: (1) PD is assessed by the investigator, (2) initiation of a new anticancer treatment, (3) death, (4) withdrawal of consent, or (5) study conclusion or early termination, whichever occurs first.

8.10.3.3 Survival Follow-up Visits

Participants who experience confirmed PD or start a new anticancer therapy will move into the Survival Follow-up Phase and should be contacted by telephone every 12 weeks to assess for survival status until death, withdrawal of consent, or the end of the study, whichever occurs first.

The Sponsor may request survival status be assessed at additional time points during the course of the study. For example, these additional time points may be requested prior to but not limited to an efficacy IA for internal decision-making and/or final analysis. All participants who are not known to have died prior to the request for these additional survival status time points will be contacted at that time.

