Duration of Participation	Each participant will participate in the study for up to approximately 2 years from the time the participant signs the informed consent form (ICF) through the final contact. After a screening phase of up to 28 days, each participant may receive assigned intervention for up to approximately 35 cycles. After the end of treatment, each participant will be followed up for 30 days for the occurrence of AEs and spontaneously reported pregnancy. All participants will be followed by telephone for OS until death, withdrawal of consent, or end of the study.						

Study Governance Committees:

Steering Committee	No
Executive Oversight Committee	No
Data Monitoring Committee	No
Clinical Adjudication Committee	No
Stage Gate Review Committee	Yes
Study governance considerations are outlined in Appendix 1.	

[figure not shown]
Study Accepts Healthy Volunteers: No

A list of abbreviations used in this document can be found in Appendix 10.

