4 STUDY DESIGN

4.1 Overall Design

This is a randomized, active-controlled, parallel group, multicenter, open-label, Phase 2 study of IT MK-1454 in combination with pembrolizumab versus pembrolizumab monotherapy in participants with a histologically or cytologically confirmed diagnosis of metastatic or unresectable, recurrent HNSCC with a tumor CPS ≥ 1 [Kulangara, K., et al 2018] as first-line

treatment. Participants need to have at least 1 measurable lesion that is amenable to IT injection for RECIST assessment.

This study will evaluate the efficacy, safety, and tolerability of IT MK-1454 in combination with pembrolizumab IV versus pembrolizumab IV alone. Figure 1 depicts a summary of the study design. Approximately 200 participants will be randomized 1:1 using IRT to receive IT MK-1454 at a dose of [CCI] in combination with pembrolizumab (Arm 1) or pembrolizumab monotherapy (Arm 2). Randomization will be stratified by PD-L1 expression level defined by CPS (≥ 1 to < 20 vs ≥ 20), ECOG performance status (0 vs. 1) and tumor HPV status (positive, negative). In Arm 1, study intervention will be IT MK-1454 [CCI] administered Q1W for 6 weeks, then Q3W, in combination with pembrolizumab 200 mg IV Q3W. In Arm 2, study intervention will be pembrolizumab 200 mg IV Q3W.

After a screening period of up to 28 days, participants will be randomized 1:1 to Arm 1 or Arm 2. Participants may be treated for up to 35 cycles (approximately 24 months) after initiation of treatment with pembrolizumab alone or in combination with MK-1454. Discontinuation Follow-Up will be 30 days after the last dose.

Participants will be treated until PD, unacceptable toxicity, or other protocol-specified criterion for cessation of treatment, at which point they will be discontinued from the study intervention. Participants who discontinue study intervention will have posttreatment follow-up for disease status (including imaging) until PD, initiating a new anticancer therapy, withdrawing consent for study participation, or becoming lost to follow-up. This protocol does not allow participants to cross over to the other arm if they experience progression.

After confirmed PD, each participant will be followed up for safety at 30 days after the EOT, then will be contacted by telephone every 12 weeks (84 ± 7 days) for survival until death, end of the study, withdrawal of consent to participate in the study, or becoming lost to follow-up, whichever occurs first.

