- No requirements for intensified management, including increased analgesia, radiation, or other palliative care

Any participant deemed clinically unstable should be discontinued from study intervention at site-assessed first radiologic evidence of PD and is not required to have repeat imaging for confirmation of PD by iRECIST.

If the investigator decides to continue treatment, the participant may continue to receive study intervention and the tumor assessment should be repeated 4 to 8 weeks later to confirm PD by iRECIST per investigator assessment. Images should continue to be sent in to the central imaging vendor for potential retrospective BICR.

Tumor flare may manifest as any factor causing radiographic progression per RECIST 1.1, including:

- Increase in the sum of diameters of target lesion(s) identified at baseline to $\geq 20\%$ and ≥ 5 mm from nadir
 - Note: the iRECIST publication uses the terminology “sum of measurements”, but “sum of diameters” will be used in this protocol, consistent with the original RECIST 1.1 terminology.
- Unequivocal progression of nontarget lesion(s) identified at baseline

- Development of new lesion(s)

iRECIST defines new response categories, including iUPD (unconfirmed progressive disease) and iCPD (confirmed progressive disease). For purposes of iRECIST assessment, the first visit showing progression according to RECIST 1.1 will be assigned a visit (overall) response of iUPD, regardless of which factors caused the progression.

At this visit, target and nontarget lesions identified at baseline by RECIST 1.1 will be assessed as usual.

New lesions will be classified as measurable or nonmeasurable, using the same size thresholds and rules as for baseline lesion assessment in RECIST 1.1. From measurable new lesions, up to 5 lesions total (up to 2 per organ), may be selected as New Lesions Target. The sum of diameters of these lesions will be calculated, and kept distinct from the sum of diameters for target lesions at baseline. All other new lesions will be followed qualitatively as New Lesions Nontarget.

Assessment at the Confirmatory Imaging

On the confirmatory imaging, the participant will be classified as progression confirmed (with an overall response of iCPD), or as showing persistent unconfirmed progression (with an overall response of iUPD), or as showing disease stability or response (iSD/iPR/iCR).

Confirmation of Progression

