9.6.1.3 Overall Survival

The nonparametric Kaplan-Meier method [Kaplan, E. L. 1958] will be used to estimate the survival curves. The treatment difference in survival will be assessed by the stratified log-rank test in participants with CPS ≥ 1 and in participants with CPS ≥ 20 . A Cox proportional hazard model with Efron's method [Efron, B. 1977] of tie handling will be used to assess the magnitude of the treatment difference (ie, the HR). The HR and its 95% CI from the Cox model with a single treatment covariate will be reported. The stratification factors used for randomization (Section 6.3.2) will be applied to both the stratified log-rank test and the stratified Cox model. Participants without documented death at the time of analysis will be censored at the date of last known contact.

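### The synopsis promises survival follow-up for every participant, but Sections 4.1 and 8.10.3.3 start it only after confirmed PD or new anticancer therapy, which omits those who stop at a first, unconfirmed PD

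*Combined protocol and SAP*

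**What the plan says.** Three places state who is contacted for survival.

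- Synopsis (1.1), Duration of Participation: "All participants will be followed by telephone for OS until death, withdrawal of consent, or end of the study". No condition on progression is attached.
- Section 4.1: "After confirmed PD, each participant will be followed up for safety at 30 days after the EOT, then will be contacted by telephone". The calls are every 12 weeks.
- Section 8.10.3.3: "Participants who experience confirmed PD or start a new anticancer therapy will move into the Survival Follow-up Phase". A second paragraph lets the sponsor ask for extra survival checks, for example before the final analysis. If it asks, everyone not known to have died is contacted.

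Four places determine who reaches confirmed PD.

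- Section 8.2.5: a clinically unstable participant stops at first radiologic PD and "is not required to have repeat imaging for confirmation of PD by iRECIST". Table 9 leaves repeat imaging in that case to the physician.
- Section 8.2.4: for a participant who stops because of documented PD, the discontinuation scan is the last one required if the investigator does not use iRECIST.
- Section 8.10.3.2, entry to imaging follow-up: "Participants who discontinue study intervention for reasons other than documented PD should continue with imaging assessments".
- Section 8.10.3.2, exit: imaging follow-up ends when the investigator assesses PD. Confirmation is not mentioned.

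On analysis, Section 9.6.1.3 states: "Participants without documented death at the time of analysis will be censored at the date of last known contact".

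The same synopsis cell also says: "Each participant will participate in the study for up to approximately 2 years from the time the participant signs the informed consent form", counted to the final contact. The synopsis puts the whole study at about 60 months.

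**The concern.** Sections 4.1 and 8.10.3.3 make survival contact depend on an event, confirmation of PD, that other sections do not require for some participants. Those left out are the ones who stopped at first PD because they were unstable, those whose investigator did not pursue confirmation, and those whose PD was found after treatment had ended, in each case with no further anticancer therapy. Their short-term risk of death is likely to be above average.

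If they are not called, their OS time is censored at about the last visit. Kaplan-Meier and Cox methods then treat them as having the same future risk as participants still under observation. Because loss of contact would be linked to deterioration, the censoring would be informative and OS would look too long. Clinical stability and further therapy are judged by open-label investigators, so the loss could also differ between arms. The documents give no basis for predicting such a difference.

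**Working it through.** The plan gives no figure to reproduce here: the readable text has no OS power or event target. The check has three parts.

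**1. Tracing participants who start no new therapy through the rules**

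| Participant | Confirmation scan required? | Imaging follow-up (8.10.3.2)? | Survival trigger in 4.1 or 8.10.3.3 met? | Covered by synopsis? |
|---|---|---|---|---|
| Clinically unstable at first PD, stops | No (8.2.5, Table 9) | No, stopped for documented PD | No | Yes |
| Stops for documented PD, investigator does not use iRECIST | No (8.2.4) | No, same reason | No | Yes |
| Stops for another reason, PD first assessed in imaging follow-up | Not stated | Ends at that assessment | No, unless confirmed | Yes |

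For the first two rows, Section 8.10.3 schedules nothing after the safety visit about 30 days after the last dose. In all three rows the synopsis and the two body sections give different answers.

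**2. Illustration of the size, under assumptions**

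From the documents: a median OS of 13.6 months for pembrolizumab monotherapy in CPS ≥1 (Section 2.2.3.2), taken as the true overall median. Assumed: the affected share f, the timing of PD, survival after PD, last contact 1 month after PD, and no sponsor-requested check.

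Model A: affected participants have OS = P + E, with P uniform on 1.5 to 6 months and E exponential with median m. The others are exponential, scaled so that the overall median is 13.6 months. Affected participants still alive at P + 1 month are censored there; everyone is censored at 36 months. Each scenario uses 200,000 simulated participants. The Kaplan-Meier median in months is:

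| f | m = 2 | m = 3 | m = 6 |
|---|---|---|---|
| 5% | 14.5 | 14.4 | 14.1 |
| 10% | 15.5 | 15.4 | 14.6 |
| 20% | 18.5 | 18.1 | 15.9 |

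At f = 10%, 7.1% to 8.9% of all participants are alive when contact stops. Of 200 randomized, that is 0.071 × 200 ≈ 14 to 0.089 × 200 ≈ 18 participants.

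Model B: exponential time to PD with median 3.5 months for everyone, median survival after PD of 2 to 4 months in the affected group, and the same overall calibration and 1-month censoring. The median reads about 14.0 (f = 5%), 14.5 (10%) or 15.4 to 16.0 (20%). The 12-month OS is overstated by about 1 to 2, 3, or 6 to 7 percentage points respectively.

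Both models give the same direction. Across them, 5% to 10% affected gives 14.0 to 15.5 months. If everyone is called, as the synopsis requires, the early censoring disappears and the bias is zero.

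**3. Stated duration of participation**

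Screening of up to 28 days, plus 34 intervals of 21 days from the first to the 35th dose, plus 30 days of safety follow-up: 28 + 34 × 21 + 30 = 772 days, or 25.4 months. This exceeds 2 years before any survival follow-up. If OS were exponential with median 13.6 months, 2^(−24/13.6) ≈ 29% would be alive at 24 months.

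**The case against.** A reader of Section 8.10.3.3 alone might infer that these participants enter no follow-up at all and that their OS is censored. The documents do not support that, for five reasons.

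- The synopsis requires telephone follow-up of all participants without condition.
- Section 7.1 says that stopping treatment is not withdrawal. It lists progression and investigator decision among the reasons for stopping while remaining monitored, with no need for confirmation, and has these participants complete the visits in the Schedule of Activities. That schedule has a survival column at about 12-week intervals. Section 8.1.9 points the same way.
- The sponsor's optional check in Section 8.10.3.3 reaches everyone not known to have died. One check before analysis would recover most of the missing deaths.
- Serious adverse events are collected to 90 days when no new therapy is started (8.4.1), so safety collection does not end at 30 days.
- The first rows of the post-treatment schedule were not readable, so a note there may settle the entry rule.

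These points stand, and they rule out calling this an established loss of OS data. They do not remove the contradiction. Section 8.10.3.3 is the section a site would consult for survival visits. The readable part of the schedule gives the timing of survival contact but no entry rule. The sponsor's check is discretionary. Section 8.4.6 exempts progression of the study cancer from safety reporting, so that route is not a reliable source of cancer deaths.

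It is also fair to object that every simulation input except the 13.6-month median is assumed. No hazard-ratio effect was calculated, and the same rule applies to both arms. A between-arm bias is therefore only a possibility.

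**Conclusion.** The concern holds as an internal contradiction in the OS follow-up rule with a foreseeable, conditional bias. The bias arises only if sites apply Sections 4.1 and 8.10.3.3 as written and the sponsor requests no general survival check. OS would then be overstated because censoring would concentrate in participants with worsening disease.

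The size cannot be derived from the documents, which give neither the affected share nor survival after PD. With 5% to 10% assumed affected, a true 13.6-month median reads about 14.0 to 15.5 months; with 20% the range is 15.4 to 18.5 months and depends heavily on the inputs. It is zero under the synopsis rule and much smaller if a check precedes the analysis.

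OS is a secondary endpoint with no hypothesis in Section 3, and the primary response-rate analysis does not depend on survival contact. The point should be corrected, but it does not threaten the trial's main conclusion. The 2-year statement is a lesser wording conflict, and no analysis uses it.

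**What to change.** - **Sections 4.1 and 8.10.3.3:** align both with the synopsis. Every randomized participant who has not withdrawn consent enters the 12-weekly survival contact when imaging follow-up ends or does not apply, whether or not PD has been confirmed or new therapy started. State the same entry rule in the post-treatment Schedule of Activities.
- **Section 8.10.3.3, second paragraph:** make the survival check of all participants not known to have died mandatory before the final OS analysis.
- **Synopsis, Duration of Participation:** reconcile the 2-year figure with up to 35 cycles of treatment and survival follow-up to death or end of study.

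The cost is amendment wording and some extra telephone calls on a schedule that already exists. No visit, procedure or treatment rule changes.
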